6.17.3. Severity

The terms “severe” and “severity” are often used to describe the intensity of a specific AE; the AE itself, however, may be of relatively minor medical significance (such as severe headache). “Severe” is not the same as “serious”, which is based on subject/event outcome or action criteria usually associated with events that pose a threat to a subject’s life or functioning.

Seriousness (not severity) serves as a guide for defining regulatory reporting obligations (for communication of urgent safety concerns). Severity, however, is a useful parameter for defining the safety profile of a product at a more-granular level of detail that will later be helpful to support a broader range of medical decision making.

The investigator is required to grade the severity or toxicity of each AE and must assess the severity of AEs according to the Common Terminology Criteria for Adverse Events (CTCAE) scale, as follows:

- **Grade 1 Mild**; asymptomatic or mild symptoms; clinical or diagnostic observations only; intervention not indicated.
- **Grade 2 Moderate**; minimal, local or noninvasive intervention indicated; limiting age appropriate instrumental activities of daily living (ADL).
- **Grade 3 Severe** or medically significant but not immediately life-threatening; hospitalization or prolongation of hospitalization indicated; disabling; limiting self-care ADL.
- **Grade 4 Life-threatening** consequences; urgent intervention indicated.
- **Grade 5 Death** related to AE.

6.17.4. Relationship/Causality

The investigator must record his/her opinion concerning the relationship of the AE to study therapy or other study intervention on the eCRF, using the categories provided therein. Investigators will determine relatedness of an event to study drug based on a temporal relationship as well as if the event is unanticipated or unexplained given the subject’s clinical course, previous medical conditions, and concomitant medications.

- **Unrelated**: Not reasonably related to the investigational product. AE could not medically (pharmacologically/clinically) be attributed to the investigational product/study treatment under study in this clinical study protocol. A reasonable alternative explanation must be available.

- **Related:** Reasonably related to the investigational product. AE could medically (pharmacologically / clinically) be attributed to the investigational product/study treatment under study in this clinical study protocol.

6.17.5. Expectedness

Expected AEs related to KNX100 treatment are provided in the KNX100 Investigator's Brochure. Based on the observation of premonitory signs of seizure in dogs dosed at ≥ 25 mg/kg/day in preclinical studies, a potential for risk of seizure in humans following administration of KNX100 has been identified. This risk is mitigated by frequent monitoring of maximum plasma exposure and observation of EEGs both prior to and post dosing. Further information is provided in the Investigator's Brochure.

An unexpected AE is any AE that is inconsistent with the nature, severity, or frequency of AEs expected as related to KNX100 treatment.

6.17.6. Suspected Adverse Reaction

Suspected adverse reaction (SAR) means any AE for which there is a reasonable possibility that the drug caused the AE; that is, there is evidence to suggest a causal relationship between the drug and the AE. This definition is taken from US FDA regulation (21 CFR 312.32(a)) but is also consistent with the Australian NHMRC (2016) guidance *Safety Monitoring and Reporting in Clinical Trials Involving Therapeutic Goods*. Emergence of IED's recorded following dose administration will be considered an SAR.

6.17.7. Suspected Unexpected Serious Adverse Reaction

A suspected unexpected serious adverse reaction (SUSAR) is an AE that individually meets criteria for an SAE ([Section 6.17.10](#)) AND for an unexpected AE ([Section 6.17.5](#)) AND for a suspected adverse reaction ([Section 6.17.6](#)).

For this study and per 21 CFR 312.32, an unexpected SAE is a SUSAR only if there is evidence to suggest a causal relationship between the drug and the AE, such as:

- A single occurrence of an event that is uncommon and known to be strongly associated with drug exposure (e.g., angioedema, hepatic injury, Stevens-Johnson Syndrome).
- One or more occurrences of an event that is not commonly associated with drug exposure but is otherwise uncommon in the population exposed to the drug (e.g., tendon rupture).
- An aggregate analysis of specific events observed in a clinical trial (such as known consequences of the underlying disease or condition under investigation or other events that commonly occur in the study population independent of drug therapy) that indicates

those events occur more frequently in the drug treatment group than in a concurrent or historical control group.

6.17.8. Follow-up of Adverse Events

All measures required for AE management and the ultimate outcome of the AE must be recorded in the source document and reported to the Sponsor.

All AEs (both serious and non-serious) should be followed until the event is resolved or explained, even if the AE causes the subject to withdraw from the study and necessitates follow-up after study withdrawal. Frequency of follow-up evaluation, and method of follow-up (either directly or through an appropriate health care option) is left to the discretion of the investigator.

6.17.9. Clinical Laboratory and Investigational Findings Adverse Events

Abnormal laboratory findings and other abnormal investigational findings (for example, on an ECG trace) should not be reported as AEs unless they are associated with clinical signs and symptoms, lead to treatment discontinuation, or are considered otherwise medically important by the investigator. If a laboratory abnormality fulfills these criteria, the identified medical condition (i.e., anemia, increased alanine aminotransferase [ALT]) must be reported as the AE rather than the abnormal value itself.

The investigator must review the laboratory report, document this review, and record any clinically relevant changes occurring during the study in the AE section of the CRF. The laboratory reports must be filed with the source documents. Clinically significant abnormal laboratory findings are those which are not associated with an underlying disease, unless judged by the investigator to be more severe than expected for the subject's condition.

All laboratory tests with values considered clinically significantly abnormal during participation in the study or within 1 day after the last dose of study drug should be repeated until the values return to normal (or baseline) or are no longer considered clinically significant by the investigator or medical monitor. If such values do not return to normal/baseline within a period of time judged reasonable by the investigator, the etiology should be identified, and the Sponsor notified.

All protocol-required laboratory assessments must be conducted in accordance with the laboratory manual and the SOA in [Appendix 1](#) and [Appendix 2](#). If laboratory values from non-protocol specified laboratory assessments performed at the institution's local laboratory require a change in subject management or are considered clinically significant by the investigator (e.g., SAE, AE, or dose modification), then the results must be recorded in the CRF.

6.17.10. Serious Adverse Events

This study will follow the definition of serious adverse events as specified in ICH E2A:

“A serious adverse event (experience) or reaction is any untoward medical occurrence that at any dose:

- *results in death,*
- *is life-threatening,*
 - *NOTE: The term "life-threatening" in the definition of "serious" refers to an event in which the subject was at risk of death at the time of the event; it does not refer to an event which hypothetically might have caused death if it were more severe.*
- *requires inpatient hospitalization or prolongation of existing hospitalization,*
- *results in persistent or significant disability/incapacity, or*
- *is a congenital anomaly/birth defect,*
- *other medically important serious medical event.”*

In deciding whether an individual event meets the definition of an SAE, the following definitions will be used:

- Life threatening means that the subject was at immediate risk of death from the event as it occurred. It does not include events that may have caused death if they occurred in a more severe form.
- Inpatient hospitalization means a medical requirement for overnight admission to hospital, due to the severity of the event and the medical requirement for inpatient treatment and/or monitoring.
- Permanent disability means a permanent and substantial disruption of a subject's ability to carry out normal life functions.
- Important medical events will be considered an SAE when, based upon appropriate medical judgment, the AE may jeopardize the subject and may require medical or surgical intervention to prevent one of the outcomes listed in this definition. Examples of such medical events include allergic bronchospasm requiring intensive treatment in an emergency room or at home, blood dyscrasias or convulsions that do not result in inpatient hospitalization, or the development of drug dependency or drug abuse.

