5.3.4. Dose Escalation

An evaluable subject is one that has been dosed, completed all assessments, and had their data reviewed by the CRC.

Blinded data to be reviewed by the CRC for each subject will include (as a minimum): PK (up to 30 hours postdose for Part A and 24 hours postdose for Part B), EEG, ECG, vital signs, pulse oximetry, neurological examination, and any adverse events.

The CRC may approve dose escalation following review of cohort data if:

- No drug related SAE's occurring within 48 hours of administration of KNX100 or placebo is observed in any subject in the dose group under evaluation.
- No drug related AE's of Grade 3 or greater are observed in 2 or more subjects within a dose group.
- The mean KNX100 C_{max} **OR** AUC does not exceed 84.9 ng/mL or 82.7 ng×h/mL respectively **and** the mean KNX100A C_{max} **OR** AUC does not exceed 26.5 ng/mL and 45.7 hr × ng/mL, respectively, the exposure associated with 1/10th of the NOEL of 2.75 mg/kg observed in the 14-day dog EEG study.
- No emergence or evidence of other PI-deemed and or medical monitor-deemed clinically significant abnormal vital signs, neurological and physical examination, or safety parameters postdose have been observed.

Dose increases will be permitted once review of data from all evaluable subjects has been performed.

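### Protocol 6.17.10: the working definition of disability is narrower than the SAE criterion the protocol adopts, so a significant but reversible incapacity may be classed as non-serious

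*Protocol*

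**What the plan says.** Protocol 6.17.10 opens with "This study will follow the definition of serious adverse events as specified in ICH E2A" and sets out the list. The disability item is an event that "results in persistent or significant disability/incapacity, or" (the final word leads to the next item).

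The section then says: "In deciding whether an individual event meets the definition of an SAE, the following definitions will be used". Four working definitions follow: life-threatening, inpatient hospitalization, disability and important medical events. The disability one is "Permanent disability means a permanent and substantial disruption of a subject's ability to carry out normal life functions". No working definition covers persistent incapacity or significant incapacity.

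Two other provisions use the classification or bear on it:

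- **Protocol 5.3.4.** The first condition for escalation is "No drug related SAE's occurring within 48 hours of administration of KNX100 or placebo is observed in any subject" in the dose group. The second concerns drug-related AEs of Grade 3 or above and fails only at two or more subjects.
- **Protocol 6.17.3.** Grade 3 includes "hospitalization or prolongation of hospitalization indicated; disabling; limiting self-care ADL". The severity scale therefore recognises disabling events without requiring permanence.

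**The concern.** The section gives two tests for one criterion. The narrower test is introduced as the one to apply, so an investigator completing an SAE form would naturally use it. An incapacity that is significant, or persistent but not permanent, meets the list and fails the working definition.

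SAE status determines:

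- **Reporting:** within 24 hours on an SAE form, or by routine eCRF entry (Protocol 6.17.11, Table 6).
- **SUSAR assessment:** only an SAE can be a SUSAR (6.17.7) and so enter the 7- and 15-day expedited routes (6.17.12).
- **The TESAE count:** part of a primary safety endpoint (Protocol 8.5.1), tabulated overall and by relatedness (SAP 6.4.1).
- **Escalation:** the first condition in 5.3.4, which a single subject can fail.

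The question is practical here. Protocol 3.2.1 names tremor, ataxia and hypoactivity as effects that preceded convulsions in dogs. Effects of that kind could incapacitate someone for a time and then resolve.

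**Working it through.** The documents state no figure on this point, so there is none to reproduce. The check is mainly a comparison of texts.

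**Step 1. The two tests.**

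| | Adopted list | Working definition |
|---|---|---|
| Term | disability/incapacity | permanent disability |
| Duration | persistent | permanent |
| Degree | significant | substantial |
| Connective | or: either suffices | and: both needed |

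Anything permanent and substantial is also persistent or significant. The reverse fails, so the working definition is strictly narrower. The other three working definitions each match a listed item. This one can match only the disability item, so it will be read as that item's definition.

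**Step 2. Other routes to SAE status.** None of these needs permanence.

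- Life-threatening events.
- Inpatient hospitalization or its prolongation. The working definition asks for a medical requirement for overnight admission to hospital. Subjects are already housed in the Phase 1 unit (Protocol 5.3), so an event observed there may not qualify.
- Important medical events: "Important medical events will be considered an SAE when, based upon appropriate medical judgment, the AE may jeopardize the subject" and may require intervention to prevent a listed outcome. A named example is "blood dyscrasias or convulsions that do not result in inpatient hospitalization". Tremor, ataxia and hypoactivity are not named, and an event that resolves under observation may not fit.

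The gap is therefore a significant, reversible incapacity that none of these routes catches.

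**Step 3. What happens in 5.3.4 to one such event, if drug-related and Grade 3.**

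- First condition (SAE within 48 hours): fails if the event is an SAE, and is met if it is not.
- Second condition (Grade 3 or above in two or more subjects): met, because there is only one.
- Third condition (exposure): not relevant.
- Fourth condition (clinically significant abnormal vital signs, neurological or physical examination, or safety parameters, as deemed by the PI or medical monitor): no subject count, so one event can fail it whatever its SAE status.

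**Step 4. Illustration of the first and second conditions alone.** Inputs: 6 KNX100 subjects per cohort (Protocol 3.1) and a per-subject probability p of such an event. The documents give no p, so it is assumed over 0.05 to 0.40, with independent subjects.

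- One event is enough: P(X ≥ 1) = 1 − (1 − p)^6
- Two are needed: P(X ≥ 2) = 1 − (1 − p)^6 − 6p(1 − p)^5
- Gap = P(X = 1) = 6p(1 − p)^5

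For p = 0.10: 1 − 0.5314 = 0.4686; gap = 6 × 0.10 × 0.5905 = 0.3543; so P(X ≥ 2) = 0.1143.

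| Assumed p | One event enough | Two needed | Gap (points) |
|---|---|---|---|
| 0.05 | 26.5% | 3.3% | 23.2 |
| 0.10 | 46.9% | 11.4% | 35.4 |
| 0.20 | 73.8% | 34.5% | 39.3 |
| 0.30 | 88.2% | 58.0% | 30.3 |
| 0.40 | 95.3% | 76.7% | 18.7 |

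The gap is an upper bound on the effect of the wording at each p. It assumes that no other SAE route, the fourth condition or CRC discretion catches the event.

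**The case against.** The mismatch is plain in the text, but much can be said against its consequences.

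- **The list still stands.** Nothing says that the definition of permanent disability replaces the listed criterion. A reader might infer that a reversible incapacity is simply not an SAE. The documents do not support that: the text is ambiguous, and other SAE routes remain. The important-medical-event route refers to preventing a listed outcome, which can lead back to the wider wording. This objection stands.
- **Escalation does not rest on the first two conditions.** A reader might infer that the bar moves from one subject to two. That is shown only when those two conditions are read alone. Ataxia, tremor or loss of power are findings that a neurological examination would be expected to detect (Protocol 6.4), and one of them can fail the fourth condition. CRC approval is also discretionary. Protocol 6.20 lets the CRC stop the study for a related significant AE in one subject, whether or not it is an SAE. This also stands.
- **Timing is a weak argument.** Permanence can rarely be judged within 24 hours of awareness or on 30-hour cohort data, but persistence cannot always be judged then either. AEs are followed until resolved or explained (6.17.8), so reclassification is possible. This largely stands, although significance, the other half of the listed criterion, can be judged at once.
- **Percentages add little.** One subject in six is 1/6 = 16.7 percentage points of TESAE incidence, but that is true of any single event and does not measure the effect of this wording. This stands.

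The inconsistency itself survives. The escalation safeguards depend on judgment, and none of them restores 24-hour SAE reporting, SUSAR assessment or the TESAE count.

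**Conclusion.** Protocol 6.17.10 is internally inconsistent. Its working definition of disability is narrower than the criterion the protocol says it follows, and it uses a term absent from that list. A significant but reversible incapacity *may* therefore be classed as non-serious.

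The conclusion assumes that an investigator applies the working definition literally and that no other SAE criterion applies. The main effect is on SAE reporting, SUSAR status and the TESAE count. The effect on escalation is secondary, because other provisions can act on a single event. How often a classification would change cannot be estimated from the documents; the 19 to 39 points above is a ceiling under assumed rates. Severity is minor to moderate: wrong as written and worth correcting.

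**What to change.** Reconcile the two texts in Protocol 6.17.10. The disability bullet should define the term actually listed, persistent or significant disability/incapacity, with the same scope: keep both adjectives and the *or*. Substituting substantial for significant, or requiring permanence, would leave a mismatch. Carry the same wording into the SAE form instructions.

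This adds no new criterion; it aligns the working definition with the one the protocol already adopts. It costs one sentence in the protocol plus an edit to the form instructions. The downside is that slightly more events may be reported as SAEs. The conditions in 5.3.4 and the SAP tabulations need no change.

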6.17.11. Reporting Adverse Events

Each AE is to be classified by the investigator as serious or non-serious (refer to [Section 6.17.10](#)). This classification determines the reporting procedures to be followed [Table 6](#).

Table 6 Reporting Requirements for Adverse Events

Gravity	Reporting Time	Type of Report
Serious	Within 24 hours	SAE form
Non-serious	Per eCRF submission procedure	AE eCRF

Abbreviations: AE = adverse event; eCRF = electronic case report form; SAE = serious adverse event.

The investigator is responsible for reporting to the Sponsor within **24 hours** of becoming aware of an event that is an SAE. Local urgent safety measures (USMs) investigated by the site must also be reported to the Sponsor within **24 hours** of becoming aware of the event.

Local reporting requirements for events that meet the Australian definitions of significant safety issues (SSIs) (including USMs) are summarized in [Appendix 6](#).

The Sponsor is responsible for assessing and categorizing the safety reports received from the investigator. Following receipt of the AE reports, the Sponsor or representative will code the events to standardized medical terminology using the Medical Dictionary for Regulatory Activities (MedDRA). During the study, all AEs will be coded to the MedDRA version that is current at the initiation visit of the first subject in the study.

The Sponsor is also responsible for communicating any important new information from investigators to the HREC and regulatory agencies, as applicable. The Sponsor activities linked to review, oversight and reporting of AEs will be conducted in compliance with applicable ICH guidelines (ICH E2A-E2F, ICH E6) both for expedited reporting of important new safety information that may arise during the study, as well as final reporting of the overall safety profile of the product at the end of the study.

6.17.11.1. Reporting Serious or Unexpected Adverse Events

The investigator is responsible for promptly reporting all SAEs to the Sponsor. The investigator will complete an SAE form and submit to the Sponsor within 1 working day after the site becomes aware of the event, irrespective of the causality or expectedness of the SAE.

The investigator is also responsible for cooperating with any Sponsor requests for further information about the SAE and responding to such requests in a timely manner to facilitate the Sponsor's fulfillment of regulatory reporting requirements. For example, typically SAE reports may require information such as a detailed description of events and investigator assessment of causality, copies of hospital reports, autopsy reports, or other relevant documents.

The Sponsor is responsible for expedited reporting of SUSARs to regulatory agencies. Expedited reporting of SUSARs will be performed in compliance with the local regulatory agency's requirements.

6.17.12. Expedited Reporting Requirements

Investigators are required to report any USMs to the Sponsor or its designee within 24 hours. The investigator will notify the HREC of SAEs and USMs, in accordance with HREC requirements and local laws and regulations. A copy of this notification must be provided to the Sponsor or its designee.

SAEs that are unexpected and considered related to the administration of the study drug will be reported by the Sponsor (or designee) to the appropriate regulatory authorities and other investigators in the form of an expedited safety report within 15 calendar days after receiving information on the SAE. The investigators will notify their reviewing HREC, and other committee(s) as required by institutional policies.

Fatal and life-threatening SUSARs will be submitted no later than 7-calendar days of first knowledge of the event and follow-up information submitted within an additional eight (8) days. The Sponsor will report any unexpected life threatening or fatal SAEs that are considered related to the investigational product to the appropriate regulatory authorities within 7 days of receiving the information.

6.17.13. Pregnancy

Pregnancies in subjects or partners must be reported to Sponsor or its designee within 24 hours of knowledge of the event up until and including the EOS visit. A subject who becomes pregnant will immediately be discontinued from study drug.

The pregnancy of a subject will be monitored for the full duration and/or followed until the outcome of the pregnancy is known.

In the event of pregnancy in the partner of a subject, the investigator should make every reasonable effort to obtain the female partner's consent for release of protected health information and notify the Sponsor or its designee within 24 hours of knowledge of the event.

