Subjects will be housed in the clinic from Day -3 prior to study drug administration and will remain in-house for 30 hours postdose (Day 2) for PK and safety assessments.

[figure not shown]
Part B (MAD) will evaluate up to 3 doses based on doses established during Part A (SAD). Each subject will receive 7 doses of study drug, administered either once (Cohorts 1 and 2) or twice daily (Cohort 3). All subjects in each MAD cohort will have their AE, PK, and electroencephalography (EEG) data, acquired up to and including Day 8, evaluated for safety and tolerability by the CRC before opening the next higher dose cohort. Subjects will be housed in the clinic from Day -3 prior to study drug administration and will remain in-house for 24 hours post morning dose (Day 8) for PK and safety assessments.

The study will be comprised of 3 periods: Screening (up to 28 days); Treatment (1 day for the SAD subjects and 7 days for MAD subjects) and Follow-up. Subjects will have a follow-up visit 7 days after the last dose. As SAD dosing is a single dose on Day 1, follow-up will occur

on Day 7. MAD dosing involves either single daily dosing (Cohorts 1 and 2) or twice daily dosing (Cohort 3) on Days 1 to 7, with a follow-up visit occurring on Day 14.

The overall study design is summarized in Figure 1. Refer to Appendix 1 and Appendix 2 for a detailed schedule of assessments.

Figure 1 Study Phases and Activities

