4.2. Inclusion Criteria

Subjects will be eligible for participation in the study only if they meet ALL of the following inclusion criteria.

None of the inclusion criteria are eligible for re-screening. No waivers will be granted and any deviation from below will be recorded as a major protocol deviation. An exception can apply for subjects who meet the inclusion and exclusion criteria, but then miss a cohort because it is filled. This would mean they are no longer eligible due to the 28-day screening window lapse. These are the only subjects that may be rescreened.

1. Ability to understand and provide written informed consent.
2. Body mass index (BMI) within the range of 18-32 (inclusive).
3. Healthy male and female volunteers ≥ 18 and ≤ 55 years old at Screening.
4. Able and willing to comply with the requirements of the study and complete the full sequence of protocol related doses, procedures, and evaluations.
5. Willing to agree not to use alcohol or recreational drugs and willing to have drug screening, prior to the first dose of KNX100 and if drug use is suspected while active in the study.
6. Willing to agree not to smoke cigarettes or use tobacco-based products prior to the first dose of KNX100 and for the entire duration of the study.

7. Males who are sexually active must use a condom OR be abstinent OR have the same sex partner OR be surgically sterile OR have partner who is of non-childbearing potential, for at least 90 days after the last dose of investigational drug. If female partner is a Woman of Child-Bearing Potential (WOCBP), the female partner must use highly effective methods of contraception, defined as below:
 - Hormonal methods of contraception including oral contraceptives containing combined estrogen and progesterone, a vaginal ring, injectable and implantable hormonal contraceptives, intrauterine hormone-releasing system (e.g., Mirena) and progestogen-only hormonal contraception associated with inhibition of ovulation.
 - Nonhormonal intrauterine device,
 - Bilateral tubal occlusion.

Refer to [Section 6.9](#) for further detail on contraception.

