6.9. Contraception

WOCBP must have a negative serum or urine pregnancy test within 24 hours prior to the start of study drug and must not be breastfeeding, lactating, or planning pregnancy during the study period. WOCBP are defined as any female who has experienced menarche and who has not undergone surgical sterilization (hysterectomy or bilateral oophorectomy) and is not postmenopausal. Menopause is defined as 12 months of amenorrhea in the absence of other biological causes. In addition, females under the age of 55 years must have a documented serum follicle stimulating hormone (FSH) level > 40 mIU/mL to confirm menopause. Male participants with potentially postmenopausal partners who are under the age of 55 years must use condoms unless their partner's postmenopausal status has been confirmed by FSH level.

WOCBP who are not exclusively in same-sex relationships and males with partners of child-bearing potential must agree to use adequate contraception. For WOCBP, contraception should be continued for 30 days after the final study visit. For males, contraception should be continued for 90 days after the final dose of study drug. In addition, males must not donate sperm for 90 days after the final dose.

Males and WOCBP who are continuously not heterosexually active are exempt from contraceptive requirements. However, WOCBP must still undergo pregnancy testing as per protocol.

Investigators will counsel WOCBP and male participants who are sexually active with WOCBP on the importance of pregnancy prevention and the implications of an unexpected pregnancy. Investigators will advise on the use of an adequate methods of contraception, which is defined as use of a condom by the male partner combined with use of a highly effective method of

contraception by the female partner. A highly effective method of contraception is one that has a failure rate of <1% when used consistently and correctly. Male participants must inform their female partners who are WOCBP of the contraceptive requirements of the protocol and are expected to adhere to using contraception with their partner.

Highly effective methods of contraception are listed below:

- Hormonal methods of contraception including oral contraceptives containing combined estrogen and progesterone, a vaginal ring, injectable and implantable hormonal contraceptives, intrauterine hormone-releasing system (e.g., Mirena) and progestogen-only hormonal contraception associated with inhibition of ovulation.

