6.15. End of Study Visit/Early Termination Visit

The End of Study (EOS)/Early Termination (ET) Visit will occur 7 days after last dose (± 2 days) for Part 1 (SAD) and 7 days after the last dose (± 2 days) for the MAD part of the study. This visit can also take place if a subject withdraws early from the study.

A serum pregnancy test will be performed for WOCBP. Hematology and coagulation, biochemistry, and urinalysis will be performed. The subject will be asked about AEs and prior and concomitant medications and an ECG will be conducted. Every attempt will be made for collection of data from withdrawn subjects via attendance to an EOS/ET Visit.

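### The duty to report pregnancies ends at the EOS visit, although the protocol's contraception periods run 30 days past that visit (women) and 90 days past the last dose (men); the rule for partners is also unclear

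*Protocol*

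**What the plan says.** **Reporting.** The first paragraph of Protocol Section 6.17.13 covers pregnancies in subjects and in partners, to be reported "within 24 hours of knowledge of the event up until and including the EOS visit". The second requires a subject's pregnancy to be followed until its outcome is known. The third deals with partner pregnancies: the investigator should seek the partner's consent for release of information and "notify the Sponsor or its designee within 24 hours of knowledge of the event". That paragraph states no end date.

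**Contraception.** Section 6.9 says: "For WOCBP, contraception should be continued for 30 days after the final study visit". It also says: "For males, contraception should be continued for 90 days after the final dose of study drug", and bars sperm donation by men for the same 90 days. The synopsis repeats the 30-day period for women. Inclusion criterion 7 (Section 4.2) repeats the period for men: "for at least 90 days after the last dose of investigational drug".

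**Timing of EOS.** Section 6.15 gives 7 days (± 2) after the last dose for the SAD part and, for Part B, "7 days after the last dose (± 2 days) for the MAD part of the study". Section 3.1 and Appendix 1 place the Part A visit on Day 7, with dosing on Day 1: "As SAD dosing is a single dose on Day 1, follow-up will occur" on that day. Appendix 1 allows ± 2 days.

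**Testing.** The last scheduled pregnancy test is at EOS: "A serum pregnancy test will be performed for WOCBP". Appendices 1 and 2 schedule no contact after it.

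**The concern.** The protocol asks subjects to avoid pregnancy for a defined time after exposure, but the stated duty to tell the sponsor about a pregnancy stops near the start of that time. The contraception periods are stated consistently in several places; only the reporting rule stops earlier.

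At stake is safety information in a first-in-human study. Following a pregnancy to its outcome depends on the sponsor knowing about it. After EOS no scheduled test or contact would bring one to light. Partners are not tested at any point, so a partner pregnancy becomes known only if someone tells the site.

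**Working it through.** The documents give no figure of their own to reproduce. The check is day arithmetic on the protocol's own periods.

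**Inputs**
- e = days from last dose to EOS. Section 6.15 gives 7 ± 2, so 5 to 9. In Part A, Day 7 (± 2) after a Day 1 dose is 6 ± 2, so 4 to 8. In Part B, Day 14 (± 2) after a last dose on Day 7 is again 5 to 9. The full range is 4 to 9, with 7 taken as nominal.
- Women: contraception ends 30 days after the final visit, which is e + 30 days after the last dose (Section 6.9).
- Men: contraception ends 90 days after the last dose (Sections 6.9 and 4.2).
- The reporting duty in the first paragraph of 6.17.13 ends at day e.

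**Share of the contraception period, counted from the last dose, that lies after EOS**
- Women: 30 / (e + 30)
- Men: (90 − e) / 90

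| e (days) | Women | Men |
|---|---|---|
| 4 | 30/34 = 88% | 86/90 = 96% |
| 5 | 30/35 = 86% | 85/90 = 94% |
| 7 (nominal) | 30/37 = 81% | 83/90 = 92% |
| 9 | 30/39 = 77% | 81/90 = 90% |

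**Counting from the first dose instead.** Part A is unchanged, because there is one dose. Part B adds 6 days to each denominator. At e = 7, women have 30/43 = 70% and men 83/96 = 86%. For e from 9 to 5 the ranges are 67-73% for women and 84-89% for men. The larger part of the period lies after EOS on either count.

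**Does another provision close the gap?**
- Section 6.17.2 requires reporting of later untoward events, but only those the PI assesses as related. An uncomplicated pregnancy is not clearly one of these.
- Section 6.17.10 counts a congenital anomaly or birth defect as serious, and Section 6.17.11.1 requires SAEs to be reported whatever their cause. These reach an adverse outcome, not the pregnancy itself.
- Section 6.18 points to a separate Study Reference Manual and Study Safety Plan for contact information only.
- The third paragraph of 6.17.13 could be read as an open-ended duty for partners. The first paragraph, however, already names partners and applies the EOS limit to them.

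None of these clearly requires an uncomplicated pregnancy first known after EOS to be reported.

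**The case against.** **A period for avoiding pregnancy and a period for reporting it serve different purposes, and nothing in the protocol says they must coincide.** This stands. The two sections do not contradict each other in the strict sense; the point is a gap in coverage.

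**The partner paragraph has no end date, so men's partners may already be covered.** This stands in part. On that reading the 92% for men would not apply. But the first paragraph of the same section sets the EOS limit for partners too, so the text supports two answers and needs clarifying.

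**The EOS limit may refer to when the pregnancy occurs, not when it becomes known.** The sentence allows both readings. If it refers to occurrence, a pregnancy that began before EOS but was recognised later must still be reported. If it refers to knowledge, that pregnancy also falls outside. On both readings, conceptions after EOS are outside the first paragraph, so the day counts are unaffected.

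**A reader might infer that pregnancies after EOS would never be reported, or that the study report would state no pregnancies when nobody had asked.** The documents do not support either. The rule ends a mandatory duty and does not bar later reports. Pregnancy is tested at screening, on admission and at EOS. The SAP text plans no pregnancy summary, so what the report would say cannot be predicted.

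**Subjects may already be told to notify the site.** This cannot be checked. The consent pages are not in the reviewed text, and the safety plan and reference manual are separate documents. Section 6.9 does require counselling on the implications of an unexpected pregnancy, but it gives no instruction to report one.

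**Conclusion.** The concern holds as a coverage gap and an ambiguity. After EOS the protocol creates no clear duty to report a pregnancy for about 30 of 37 days after the last dose in women (81%, range 77-88%) and about 83 of 90 days in men (92%, range 90-96%). For partners, Section 6.17.13 is also unclear within itself.

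It would go too far to say that almost all of the period is excluded for women; about four fifths is.

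The figures rest on three assumptions: EOS takes place within its stated window, the EOS limit in the first paragraph of 6.17.13 governs partners, and the contraception periods in 6.9 are taken as given. A subject seen early at an ET visit could have a different interval. The percentages count calendar days, not expected pregnancies. The documents give no rate from which to estimate missed events, and with about 64 subjects and required contraception, few would be expected. The case for change rests on the value of each such report in a first-in-human study and the low cost of the change.

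**What to change.** Reconcile Section 6.17.13 with Section 6.9:
- Let the pregnancy reporting period, for subjects and for partners, run at least to the end of the contraception periods already stated in 6.9.
- Make the first and third paragraphs of 6.17.13 agree on that end date, and say whether it refers to when the pregnancy occurs or when it becomes known.
- Tell subjects at EOS to notify the site of any pregnancy in that time, with matching consent wording if it is not already there.

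At nominal timing, reporting after the last dose would lengthen from about 7 to about 37 days for women (range 34 to 39; 30 days added) and to 90 days for men's partners (about 83 days added, range 81 to 86).

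The change is to wording only. It adds no visits or tests and leaves the contraception requirements as they are. The small cost is that the site must accept and pass on late notifications for up to 90 days after the last dose.
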